Potential participants will be identified via screening and then recruited. Screening will involve applying the selection criteria to the Medicaid claims and HIV surveillance data to identify potential participants. We will screen for potential participants given the study's goal is real-time identification of Medicaid members living with HIV and at early risk of falling out of care (as indicated by a late ART prescription refill(s)). Potential participants identified via screening will then be recruited. A simple schematic of screening and recruitment processes for potential participants is shown in **Figure 2**. Screening and recruitment will occur according to existing interagency and contractual agreements, which will collectively authorize Virginia Commonwealth University (VCU) personnel to implement and evaluate the AIMS program for evidence-based quality improvement on behalf of Virginia Medicaid.

Figure 2. Schematic of screening and recruitment for eligible potential participants

Screening will involve: 1) Initial identification of eligible potential participants using the Medicaid claims, and 2) Data integration with HIV surveillance data and confirmation of potential program participant eligibility. Screening activities will occur on a monthly basis during study enrollment, which is anticipated to be 6 months.

Initial eligibility. We will use the Medicaid claims to identify a preliminary sample of eligible potential participants. We will select from the Medicaid claims those enrollees who satisfy inclusion criteria: current enrollment in Virginia Medicaid, continuous Virginia Medicaid enrollment for >9 months, current

age 19–64 years, non-dual eligible for Medicare, identified as living with HIV according to the HIV case identification algorithm (Aim 1), and a late ART prescription refill(s) by >30–365 days in the prescription claims. ‘Late ART prescription refill(s) by >30–365 days’ refers to the most recent ART prescription(s) that is >30–365 days in the prescription claims after the expected date of refill or renewal.

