We will exclude enrollees who have a record of third-party health insurance during the past 3 months. We will exclude enrollees who have a missing phone number and/or mailing address. We will exclude those experiencing within-class ART switches due to medication toxicity (defined as a new within-antiretroviral class ART prescription claim >30 days of the expected date of ART prescription refill or renewal). We will also exclude those enrollees experiencing ART resistance and thus switching to a new regimen (defined as a claim for an antiretroviral drug in a new ART class occurring >30 days of the expected date of ART prescription refill or renewal). We will exclude enrollees whose linked HIV provider is a provider practicing at a facility offering PositiveLinks. The study will exclude enrollees who do not have a record in Virginia’s HIV surveillance data, as a record in the HIV surveillance data confirms HIV status. The study will exclude enrollees who do have a record of an ART prescription(s) in the Virginia HIV surveillance data, but did not have a record of an ART prescription(s) in the claims data, as an additional confirmatory check on study eligibility. We will exclude enrollees who do not speak English, as PositiveLinks has not been validated in languages other than English.

An initial database of eligible potential participants will be constructed and include: first and last name, social security number, complete or partial address, race/ethnicity, sex at birth, and date of birth; and expected date of ART prescription fill, refill, or renewal; and an indicator for a late ART prescription refill(s) by >30–365 days). Analysis will be conducted by authorized VCU personnel and saved on the Virginia Medicaid servers per an amendment to an existing Interagency Agreement between Virginia Medicaid and VCU.

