Confirmed eligibility. The initial database of eligible potential participants will be integrated with an extract of HIV surveillance data from the Virginia Department of Health. The integrated data will be used to confirm HIV status of eligible potential participants, their current/prior ART prescription(s) from state health department program databases, and potential participant eligibility for the study. Authorized Virginia Medicaid personnel will securely transfer the initial database of eligible potential participants to the Virginia Department of Health per an existing Interagency Agreement. Data integration and potential program participant eligibility will occur on a monthly basis during the enrollment period. After data transfer, authorized VCU personnel will use deterministic and probabilistic methods to link the two databases using the following variables: first and last name, social security number, complete or partial address, race/ethnicity, sex at birth, and date of birth. We note that complete information about current or prior ART prescriptions, which we are using to confirm potential participant eligibility where possible, is not available for all Virginians living with HIV; this is because only some Virginians have accessed state programs providing antiretroviral prescriptions. Given Medicaid’s comprehensive ART prescription coverage, we anticipate that Virginia Department of Health databases with ART prescription will be used primarily to ascertain if a potential participant has previously received ART prescriptions.

Recruitment

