Phases 1 and 2	Date of final phase 2 consultation or joining of PositiveLinks*

* Most recent date will be selected; does not include direct messaging support provided via PositiveLinks.

Outcomes

Outcomes will be at the participant level. The primary outcome will be HIV viral suppression, defined as the most recent HIV RNA viral load <200 copies/mL at 3-month follow-up. In the usual care arm, 3-month follow-up will be the first date an eligible control is confirmed as having a late ART prescription refill(s) by >30–365 days; in the program arm, 3-month follow-up will be as shown in Table 1. The secondary outcomes will be adherence (defined as the proportion with ART prescription claims covering >90% of enrolled coverage days) and the number and percentage of participants reinitiating late ART prescription.

Statistical analysis

Descriptive statistics. We will evaluate the balance of demographics and other patient characteristics, as well as the measures between the 2 treatment groups (those enrolled in the Program arm, and those in the Usual Care [control] group). We will compare the means and medians of the continuous variables and test the differences between the treatment samples using t-tests and Kruskal-Wallis tests. Systemic differences between the enrolled participants enrolled and the control might introduce selection bias.

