inclusion and Virginia Medicaid–Virginia Department of Health matching protocols, we note that no missing data are allowed.

Other data and analyses

Other data to be collected through interactions with participants include the quality improvement initiative's process data. These data will be used to track study progress and facilitate recruitment and enrollment (e.g., number and timing of contact attempts, mailing address for optional certified letter), current ART use to determine final eligibility (i.e., confirmation that the participant has not refilled their ART prescription), and barriers discussed and referrals made.

Additionally, PositiveLinks app metadata and usage data will be collected through the PositiveLinks app. App metadata include: number of app launches, number of app log ins, response rates for daily queries about medication, response rates for daily queries about mood, response rates for daily queries about stress, response rates for weekly quizzes, number of posts to community message board, number of direct messages to linkage coordinator, and number of times visiting resources section. The text of community board posts will also be collected.

Descriptive statistics will be used to summarize recruitment and enrollment, barriers endorsed, referrals made, and PositiveLinks app usage. We may examine correlates of these variables and/or consider these variables as confounders in the primary evaluation analyses. Community board posts from the PositiveLinks app will be examined using textual analysis methods.

Data management

Data management and statistical analysis will be performed using Terradata 16.10, REDCap 10.9.4, and SAS® Software version 9.4 (or most recent VCU- and agency-approved software releases available). Statistical analysis will occur at Virginia Medicaid, Virginia Department of Health, VCU, University of Virginia, and CDC. Intermediate datasets will be stored on Virginia Medicaid servers, Virginia Department of Health servers, and University of Virginia servers. Final limited and de-identified datasets will be stored at Virginia Medicaid, as well as Virginia Department of Health, and also securely transferred to VCU and CDC.

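### Lateness and adherence are read from prescription claims only, so a person on provider-administered ART billed as a medical claim can be entered as late and scored non-adherent while virally suppressed

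*Combined protocol and SAP*

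**What the plan says.** Under Screening (Initial eligibility), candidates come from the Medicaid claims, but the inclusion criterion is "a late ART prescription refill(s) by >30–365 days in the prescription claims", and the definition that follows says that a late refill "refers to the most recent ART prescription(s) that is >30–365 days in the prescription claims after the expected date of refill or renewal". Both statements confine lateness to prescription claims.

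Two switch exclusions follow, and they are worded differently. The within-class switch is "defined as a new within-antiretroviral class ART prescription claim >30 days of the expected date of ART prescription refill or renewal". The switch to a new class is "defined as a claim for an antiretroviral drug in a new ART class occurring >30 days of the expected date", with no limit to prescription claims.

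Under Procedures: Program arm, the check about ten business days after a Phase 1 referral also looks for an ART prescription claim. Under Outcomes, adherence is "the proportion with ART prescription claims covering >90% of enrolled coverage days". Reinitiation is "the number and percentage of participants reinitiating late ART prescription", with no data source named. The primary outcome, viral load below 200 copies/mL, does not depend on how ART was billed.

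Two further checks exist. Health department ART records are consulted, but the Confirmed eligibility text calls them incomplete: "this is because only some Virginians have accessed state programs providing antiretroviral prescriptions". Other data and analyses lists, among data collected through interactions with participants, "current ART use to determine final eligibility (i.e., confirmation that the participant has not refilled their ART prescription". Procedures: Usual care arm says that controls are not contacted at all. No section says how ART billed outside the prescription claims is treated.

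**The concern.** The entry rule and the adherence outcome share one blind spot, and the primary outcome does not have it. Someone in continuous treatment through a route that leaves no prescription claim looks the same at entry as someone who has stopped. At follow-up the same person can be a success on viral suppression and a failure on adherence, for a reason unrelated to the program.

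If such people remain more often among controls than among participants, the comparisons are biased in opposite directions: against the program on suppression, and in its favor on adherence and probably reinitiation. A split between the primary and secondary results could then reflect billing route, and the analysis would have no way to tell. The propensity score covariates named in the Statistical analysis section (age, gender, race, enrollment, provider specialty, hospital, geography) do not include the route by which ART is supplied.

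**Working it through.** **Step 1: follow one person through the rules.** Suppose a person with earlier pharmacy fills moves to provider-administered ART, billed as a medical claim, on the date the next fill is due.

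- *Lateness:* no new prescription claim appears, so from day 31 the most recent fill is more than 30 days late. The rule is met until day 365.
- *Within-class exclusion:* it needs a prescription claim, so it does not apply.
- *New-class exclusion:* it needs a claim of unspecified type, in a new class, more than 30 days from the due date. It can apply if medical claims are searched, the class is new and a later dose is billed in that window.
- *Health department records:* they help only if the person used a state program. The exclusion for ART in surveillance data but none in claims would not remove someone whose earlier fills are in the claims.
- *Current-use check:* it may remove the person in the program arm, although its stated aim is to confirm that no refill occurred. It cannot operate for a control.
- *Adherence over follow-up:* no prescription claim covers any day, so the person fails.
- *Reinitiation:* a failure if it is read from prescription claims, which is likely but not stated.
- *Suppression:* can be met if the treatment is working.

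**Step 2: the plan's own figure.** Sample size and statistical power considerations gives 50% control suppression, 100 controls, 100 program participants, a .28 difference and more than 80% power. With a two-sided 5% test (assumed, since the plan gives no alpha) and 78% in the program arm, the pooled proportion is 0.64:

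power = Φ[(0.28 − 1.96·√(2·0.64·0.36/100)) / √((0.50·0.50 + 0.78·0.22)/100)] = Φ[(0.28 − 0.1330)/0.0649] = Φ(2.26) = 98.8%.

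The statement of more than 80% is therefore met. The 350 per arm in the same paragraph is not reproduced (45 per arm gives 80% power). That is a separate matter and is not used here.

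**Step 3: size of the distortion.** Let q be the share of apparently late people who are in fact on such ART. Assumptions not in the documents: q = 2%, 5% or 10%; 90% of these people are suppressed; they gain nothing from the program. The 50% rate from the plan is applied to the other controls.

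- Control suppression = 0.50(1 − q) + 0.90q = 0.50 + 0.40q.
- Difference, controls only affected = 0.78 − (0.50 + 0.40q) = 0.28 − 0.40q.
- Difference, equal q in both arms = 0.28(1 − q).

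| q | Control suppression | Shift (points) | Difference, controls only | Difference, both arms |
|---|---|---|---|---|
| 2% | 50.8% | +0.8 | 27.2 | 27.4 |
| 5% | 52.0% | +2.0 | 26.0 | 26.6 |
| 10% | 54.0% | +4.0 | 24.0 | 25.2 |

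With no true effect, 10% in controls only gives a spurious difference of −3.5 to −4.5 points when suppression among the misclassified is 85% to 95%. Equal shares in both arms give none.

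**Step 4: secondary outcomes in controls.** If a share a of the other controls is adherent, measured adherence is a(1 − q), a relative fall of 2%, 5% or 10%. If reinitiation is read from prescription claims and 40% of the others reinitiate (assumed), measured reinitiation is 0.40(1 − q) = 39.2%, 38.0% or 36.0%, a fall of 0.8, 2.0 or 4.0 points.

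**Step 5: power at 100 per arm, q = 10%, suppression 85% to 95% among the misclassified.** At a true difference of .28, power is about 95% to 96% if only controls are affected and about 97% if both arms are. At a true difference of .193, the smallest detectable with 80% power, it falls to 58% to 63% (controls only) or 72% to 73% (both arms).

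**The case against.** The strongest reply is that the premise lies outside the documents. Nothing in them says that any Virginia Medicaid enrollee receives ART billed as a medical claim, and the Confirmed eligibility text refers to comprehensive Medicaid prescription coverage of ART. That stands as a limit on size: q is unknown and could be negligible. It does not change what the definitions count.

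Several stronger readings are tempting but not supported:

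- *That everyone on such ART is entered as late because neither switch exclusion applies.* The new-class exclusion is worded broadly enough to remove some of them, and repeat doses could fall in its window. People with no earlier prescription claim, or a gap over 365 days, would not enter at all.
- *That they are certainly scored as not reinitiated.* No source is named for that outcome.
- *That the bias is necessarily directional.* Controls are screened by the same criteria, so equal shares would mainly dilute the effect. The argument for concentration in controls rests on the current-use check, which depends on contact.
- *That inpatient or residential stays act the same way.* A stay would have to delay a fill by more than 30 days to create entry, and a fill after discharge could count as reinitiation. The Program arm text lists substance use and mental health as barriers to discuss, and does not mention stays.

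It is also fair that 0.8 to 2.0 points, at q of 2% to 5%, is small against a planned difference of 28 points.

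**Conclusion.** The point holds as a gap in measurement. As written, ART billed as a medical claim is not counted in lateness, the within-class exclusion, the Phase 1 refill check or adherence, so a treated and suppressed person can be entered as late and scored non-adherent. The existing checks close this only in part, and the one that asks about current use cannot reach controls, so residual error would tend to sit there.

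On the stated assumptions (2% to 10% of controls only, 90% against 50% suppressed) control suppression rises by 0.8 to 4.0 points. That would not defeat a trial with a true 28-point effect. It matters more for a smaller effect, and for interpreting any disagreement between suppression and adherence. Suppression in this group is itself an inference about people in continuous treatment, and the share affected has to come from the claims. The change is worth making because it is cheap.

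**What to change.** Define ART exposure as any Medicaid claim for an antiretroviral, whether a pharmacy claim or a medical or procedure claim for a provider-administered product. Use that definition for lateness, both switch exclusions, adherence and reinitiation, and name it as the data source for reinitiation. Prespecify a days-covered rule for provider-administered products. Treat a person with such coverage at screening as not late. Reconcile the wording of the two switch exclusions, and say whether the Phase 1 refill check uses the same claims.

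Apply the same claims-based rule in both arms, so that eligibility does not rest on a check available in one arm only. Because control data are to be de-identified with no code key, the coverage flag should be derived before that step. Reporting by arm how many people the rule removes would show the actual share.

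The cost is a code list, a query on the Medicaid claims and protocol wording. The eligible pool shrinks by an amount that the documents do not allow one to estimate. Removing inpatient or residential days from the adherence calculation is an optional convention; if adopted, it should be stated in advance and used in both arms.

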Courtesy notification letter and information sheet for providers. A courtesy notification letter and study information sheet will be securely faxed to each participant's primary HIV provider. If attempts to fax a provider are unsuccessful, a courtesy notification letter and study information sheet will be mailed to the provider. Contact information for providers will come from the Medicaid claims, the National Provider and Plan Enumeration System (NPPES) Provider Lookup tool (<https://npiregistry.cms.hhs.gov/>), the Virginia Board of Medicine practitioner and license databases (<https://www.vahealthprovider.com/index.asp>), and/or via an online search. The letter will briefly summarize the study, indicate that the provider has one or more patients with a late ART prescription refill(s) >30–365 days, and note that the study team has contacted the participant on behalf of Virginia Medicaid. The letter is intended as a courtesy notification to providers, in line with traditional health department Data to Care program activities involving patient contact. We emphasize that names of the provider's patient participants will not be listed in the letter. The letter will be accompanied by a more detailed information sheet about the study. Courtesy notification letters and information sheets will be sent monthly during the study's enrollment period. A provider will receive up to one courtesy notification letter, regardless of the number of patient participants.

Program implementation. Patient-level support for the program arm will occur in up to two phases. These phases will be defined by the number of days an ART prescription(s) fill is late—either >30–60 days or >60 days after the expected fill date. Operationally, the phases will be distinguished by the barriers focused on during the phone consultation and the level of support offered to participants. Study

enrollment can occur in either phase. Both phases will involve phone consultations to discuss participant barriers to timely filling of ART prescriptions and referrals to resources to address these barriers. The phone consultations will be delivered by a linkage coordinator. Detailed information on each phase follows.

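### Third-party cover is checked for only 3 months, so some controls with a long last fill under another payer can be coded late when they are not, and only the program arm has a check that could catch this

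*Combined protocol and SAP*

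**What the plan says.** The Initial eligibility part of the Screening section takes lateness from Medicaid prescription claims: it "refers to the most recent ART prescription(s) that is >30–365 days in the prescription claims after the expected date of refill or renewal". Two rules concern coverage. Enrollees need "current enrollment in Virginia Medicaid, continuous Virginia Medicaid enrollment for >9 months", and the exclusions that follow state: "We will exclude enrollees who have a record of third-party health insurance during the past 3 months". No rule addresses other insurance that ended more than 3 months ago.

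Days late also sets the phase of support. Under Program implementation the phases are "either >30–60 days or >60 days after the expected fill date".

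Two checks bear on whether a coded gap is real:

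- Confirmed eligibility links the Medicaid list to health department data to confirm HIV status, "their current/prior ART prescription(s) from state health department program databases, and potential participant eligibility for the study". The same section says that the ART information, "which we are using to confirm potential participant eligibility where possible, is not available for all Virginians living with HIV", because only some people have used the state programs.
- Other data and analyses lists, among data gathered through interactions with participants, "current ART use to determine final eligibility (i.e., confirmation that the participant has not refilled their ART prescription".

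Procedures: Usual care arm applies the same screening to controls but rules out any contact with them.

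**The concern.** A gap in Medicaid claims measures a gap in treatment only if Medicaid would have seen every fill since the last claim. The sponsor evidently accepts this, since it excludes people with recent other insurance. But the look-back for that exclusion is a fixed 3 months, while the gap being measured can run to 365 days beyond the expected refill date. A person who obtained ART through another insurer, and whose cover ended just outside the 3 months, passes the exclusion and is dated from an older Medicaid claim.

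Two errors could follow: someone not yet more than 30 days overdue enters the study, or someone in the Phase 1 range is coded as Phase 2. The first matters more for inference. Such people have been on treatment until recently and are probably suppressed. In the program arm the refill confirmation may remove them; in the control arm nothing does. Control suppression would rise and the estimated effect would fall. Reinitiation, a secondary outcome, is exposed in the same way, because a control's next routine fill under Medicaid could count as a restart.

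**Working it through.** The plan gives no figure for misclassified lateness, so there is none to reproduce. The check is date arithmetic.

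**Inputs from the plan.** Third-party look-back 3 months; continuous enrollment >9 months; eligibility cut 30 days late; phase cut 60 days late; control suppression 50% and detectable difference 0.28 (Sample size and statistical power considerations).

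**Assumptions.** One month = 30.44 days, so 3 months ≈ 91 days and 9 months ≈ 274 days. Days' supply is not stated; 30, 60 and 90 days are used. Fills paid by another insurer leave no Medicaid claim.

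**Third-party rule.** The last outside fill was made at least 91 days before screening, and no Medicaid ART fill followed. Minimum true lateness = 91 − days' supply:

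- 30-day fill: 91 − 30 = 61 days. Truly late, and already past the 60-day phase cut.
- 60-day fill: 91 − 60 = 31 days. Truly late, but possibly in the Phase 1 range.
- 90-day fill: 91 − 90 = 1 day. Possibly not late by the study's definition.

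True lateness of 30 days or less therefore needs an outside supply above 91 − 30 = 61 days. True lateness of 60 days or less, coded as Phase 2, needs a supply above 91 − 60 = 31 days.

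**Width of the slot.** For a 90-day fill, true lateness is 30 days or less only if the fill was made between about 91 and 30 + 90 = 120 days before screening. It is 60 days or less if the fill was made between about 91 and 60 + 90 = 150 days before screening.

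**Example.** A Medicaid supply ran out 335 days ago. Other cover then paid for ART and ended 3.2 months (97 days) ago with a final fill on that date. The coded lateness is 335 days. The true figure is 97 − 90 = 7 days after a 90-day fill, which is false eligibility. After a 30-day fill it is 97 − 30 = 67 days, which leaves both eligibility and phase unchanged.

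**Enrollment rule.** With 274 days enrolled, no Medicaid ART fill and no other cover in that time, true lateness is at least 274 − 30 = 244, 274 − 60 = 214 or 274 − 90 = 184 days. All exceed 60, so neither eligibility nor phase is wrong.

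**Illustration of size (assumed inputs, not estimates).** If a fraction f of controls is falsely late with suppression s, the control rate is 0.50 + f(s − 0.50).

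- f = 0.05, s = 0.80: 0.50 + 0.05 × 0.30 = 0.515; difference 0.78 − 0.515 = 0.265.
- f = 0.20, s = 0.90: 0.50 + 0.20 × 0.40 = 0.58; difference 0.78 − 0.58 = 0.20.

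These assume that the refill confirmation removes every such person from the program arm. If it removed none and both arms had the same f, the difference would be (1 − f) × 0.28, or 0.266 to 0.224. The effect is diluted either way.

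**The case against.** The strongest reply is that the affected group is narrow. Ordinary 30-day fills produce neither error, and 60-day fills cannot produce false eligibility. Even with a 90-day fill, the dispensing date must fall in about a one-month slot, and the person is still 1 to 30 days overdue. This stands, and it is why the effect is probably small.

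It can also be said that the mechanism is assumed. Given "continuous Virginia Medicaid enrollment for >9 months", other cover held 3 to 9 months ago must have run alongside Medicaid, and the documents do not say that such fills leave no Medicaid claim. That is fair as a caveat. But if Medicaid saw those fills, the existing third-party exclusion would have little purpose here.

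The existing checks answer part of the point. The refill confirmation targets people who are actually on ART, but it depends on contact and so cannot reach controls. The state data cover only users of state programs. The exclusion of people with an ART record in surveillance data but none in claims does not catch someone with an old Medicaid claim. Matching might help, but past third-party cover is not among the covariates named under Statistical analysis.

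A reader might infer something stronger: with 30-day fills the 3-month check spans the whole gap only up to 61 days late, leaving 365 − 61 = 304 of the 335 eligible values (91%) not fully covered, and the 9-month rule leaves 121 (36%) or 181 (54%) for 30- or 90-day fills. These are shares of possible lateness values, not of people. For most of them the person is truly late and in the right phase, and the documents attach no further rule to exact days late beyond 60.

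**Conclusion.** The point holds in limited form. The third-party look-back is shorter than the gap it should protect, and a long last outside fill can produce a falsely late person or a wrong Phase 2 coding. The consequence is unequal between arms, because the only check that could catch a privately paid fill works through participant contact.

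The expected direction is an understated program benefit, if falsely late controls are mostly suppressed. The size cannot be derived: the documents give neither days' supply nor the share of enrollees with other cover that ended 3 to 12 months before screening. Under the assumed inputs shown, a 28-point difference would shrink by 1.5 to 8 points. The narrow slot suggests that the true loss is small.

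Two further inferences are not supported. The enrollment rule does not by itself create false lateness or a wrong phase; it can only overstate how late a truly late person is. And nothing shows that the estimate would be reversed, which would need a true effect smaller than the shift. This is an inexpensive improvement to make, not a flaw that invalidates the comparison.

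**What to change.** In the screening query for both arms, exclude anyone with third-party health insurance recorded at any time from the most recent Medicaid ART fill to the screening date, with the present 3 months as a minimum.

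If a fixed look-back is preferred, set it to the lateness cut plus the longest days' supply in use. For 90-day fills that is 30 + 90 = 120 days to protect the eligibility cut, or 60 + 90 = 150 days to protect the phase cut as well.

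If losing eligible people is a concern with an expected program arm of 100, keep the present rule and repeat the primary analysis excluding people in both arms with other cover recorded since the last Medicaid fill. In either case, state that the refill confirmation has no counterpart among controls. The enrollment rule needs no change on this account.

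The cost is one changed condition in an existing query. The sponsor should confirm that third-party history older than 3 months is available. The main downside is that some truly late people with recent other cover are excluded, including any whose other insurance did not pay for ART.
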